# 15.3. Pharmacokinetic Statistical Analysis

Visterra Insert
Customer Name/ Logo
Protocol VIS954-101
Page 29 of 42

Statistical Analysis Plan

# 16. PHARMACODYNAMIC ANALYSIS

# 16.1. Pharmacodynamic Measurements

The PD analysis will be based on the PDAS. A listing of PD blood sample collection dates and times will be provided for PD testing of Complement 5a receptor 1 (C5aR1) Receptor Occupancy (RO; VIS954 binding). For all PD endpoints, participant listings of all observed data over time will be presented by treatment.

%RO Neutrophils  $\frac{\text{CCI}}{\text{CCI}}$  are the primary PD endpoints of interest and will be summarized using descriptive statistics by treatment group. Figures of mean %RO over time data will be presented with error bars (defined as mean  $\pm$  SD) by treatment group. Similarly, figures of median %RO over time data will be presented by treatment group. Individual observed %RO over time data for each participant will be graphically presented separately for each treatment group. Baseline data will be taken as the last measurement prior to dosing.

#### CC

- Time spent above 40% RO, defined as duration in hours from date and time of dosing until the date and time of PD collection when %RO > 40%
- CCI

Each derived PD variable above will be listed by participant and summarized with descriptive statistics by treatement group.

Visterra Insert
Customer Name/ Logo
Protocol VIS954-101
Page 30 of 42

Statistical Analysis Plan

[figure not shown]
# 16.2. Pharmacodynamic Parameters

Not applicable to this study.

# 16.3. Pharmacokinetic-Pharmacodynamic Relationships

Not applicable to this study.

# 18. SAFETY OUTCOMES

All outputs for safety outcomes will be based on the SAF.

There will be no statistical comparisons between the treatment groups for safety data, unless otherwise specified with the relevant section.

### 18.1. Adverse Events

Definitions of AE, unsolicited AE, and solicited AE can be found in Section 10.3 of the clinical study protocol. Unsolicited Adverse Events (AEs) will be coded using MedDRA central coding dictionary, version 26.1.

Treatment-emergent adverse events (TEAEs) are defined as AEs that first occur or worsen in severity after the study medication administration, and up to Day 71 (including the follow-up period) after the study medication administration.

Pretreatment AEs are defined as AEs occurring prior to dosing. These events will be presented in the listings only and will not be included in the tabular summary of AEs.

See Appendix 2 for handling of partial dates for AEs. In the case where it is not possible to define an AE as treatment emergent or not, the AE will be classified by the worst case, i.e., treatment emergent. Solicited AEs are predefined local injection site reactions and systemic events for which the participant is specifically questioned, and responses recorded in the eCRF data. These are collected at predefined timepoints of 1 and 4 hours post dose (Day 1), 24 hours post dose (Day 2), and on Days 3 and 29 for tenderness, pain, erythema/redness, and induration/swelling with responses based on the severity of each condition as Mild, Moderate, Severe, or Potentially Life-threatening.

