The study will be conducted in 6 sequential cohorts. Each cohort will enroll 9 participants, randomized to VIS954 or placebo at a ratio of 7:2 (7 VIS954:2 placebo). Each cohort will also optimally enroll 5 non-Japanese participants and 4 Japanese participants (achievement of this ratio is desired but not mandatory to advance to the next cohort). No more than one Japanese participant per cohort may be randomized to receive placebo.

Potential participants will be carefully screened for eligibility prior to study enrollment.

On Day 1, a single dose of VIS954 or placebo will be administered SC.

Sentinel participants will be utilized in each cohort; the first 2 non-Japanese participants in each cohort will be randomized to receive either VIS954 (n = 1) or placebo (n = 1) and will receive the study intervention at least 24 hours before the remaining 7 participants in the cohort are dosed. The safety data from each of the 2 sentinel participants will be reviewed over the 24-hour postadministration period to determine whether it is

appropriate to proceed with dosing of the remaining participants in the cohort as planned. A similar review will occur for each dose escalation. The remaining 7 participants in a cohort will be randomized to receive VIS954 (n = 6) or placebo (n = 1).

Escalation to next dosing level will occur after review of blinded safety data when at least 7 participants have completed \geq 14 days in a cohort.

The planned dose of VIS954 for each cohort is summarized in the table below.

Study Intervention for Each Cohort						
Cohort	Study Intervention					
Cohort 1	VIS954 or placebo					
Cohort 2	VIS954 or placebo					
Cohort 3	VIS954 or placebo					
Cohort 4	VIS954 or placebo					
Cohort 5	VIS954 or placebo					
Cohort 6	VIS954 or placebo					

Brief Summary:

This FIH study will assess the safety, tolerability, PK, and PD of VIS954.

The study is comprised of:

- A screening visit up to 28 days before dosing
- An in-house stay for 4 days, with admission to the study center on Day −1, SC administration on Day 1, and discharge on Day 3
- A postdose period with outpatient visits on Days 5 (± 2 days), 8 (+ 1 day), 11 (± 1 day), 15, 22, 29, 36, 43, and 57 (for all visits not otherwise specified, ± 3 days)
- A final follow-up visit on Day 71 (± 3 days)

Number of Participants:

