4.1 Overall Design

This is a phase 1, randomized, placebo-controlled, double-blind, single ascending dose, FIH study to assess the safety, tolerability, PK, and PD of VIS954 administered SC in healthy participants.

The study will be conducted in 6 sequential cohorts. Each cohort will enroll 9 participants, randomized to VIS954 or placebo at a ratio of 7:2 (7 VIS954:2 placebo). Each cohort will also optimally enroll 5 non-Japanese participants and 4 Japanese participants (achievement of this ratio is desired but not mandatory to advance to the next cohort). No more than one Japanese participant per cohort may be randomized to receive placebo.

The study is comprised of:

- A screening visit up to 28 days before dosing
- An in-house stay for 4 days, with admission to the study center on Day −1, SC administration on Day 1, and discharge on Day 3
- A postdose period with outpatient visits on Days 5 (± 2 days), 8 (+ 1 day),
 11 (± 1 day), 15, 22, 29, 36, 43, and 57 (for all visits not otherwise specified, ± 3 days)
- A final follow-up visit on Day 71 (± 3 days)

The total duration of the clinical study per participant will be up to 102 days (approximately 4 months), including the screening period.

Potential participants will be carefully screened for eligibility prior to study enrollment.

On Day 1, a single dose of VIS954 or placebo will be administered SC.

Sentinel participants will be utilized in each cohort; the first 2 non-Japanese participants in each cohort will be randomized to receive either VIS954 (n = 1) or placebo (n = 1) and will receive the study intervention at least 24 hours before the remaining 7 participants in the cohort are dosed. The safety data from each of the 2 sentinel participants will be reviewed over the 24-hour postadministration period to determine whether it is appropriate to proceed with dosing of the remaining participants in the cohort as planned. A similar review will occur for each dose escalation. The remaining 7 participants in a cohort will be randomized to receive VIS954 (n = 6) or placebo (n = 1).

Escalation to next dosing level will occur after review of blinded safety data when at least 7 participants have completed \geq 14 days in a cohort.

The planned dose of VIS954 for each cohort is summarized in Table 4.1-1.

Table 4.1-1 Study Intervention for Each Cohort						
Cohort	Study Intervention					
Cohort 1	VIS954 or placebo					
Cohort 2	VIS954 or placebo					
Cohort 3	VIS954 or placebo					

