8.4.1 Time Period and Frequency for Collecting AE and SAE Information

All AEs and SAEs will be collected from the signing of the ICF until the last visit as specified in the Schedule of Assessments (Table 1.3-1).

Medical occurrences that begin before the start of study intervention but after obtaining informed consent will be recorded as Medical History / Current Medical Conditions, not as AEs.

All SAEs will be recorded and reported to the sponsor or designee immediately and under no circumstance should this exceed 24 hours, as indicated in Section 10.3. The investigator will submit any updated SAE data to the sponsor within 24 hours of it being available.

Investigators are not obligated to actively seek information on AEs or SAEs after conclusion of the study participation. However, if the investigator learns of any SAE, including a death, at any time after a participant has been discharged from the study, and he/she considers the event to be reasonably related to the study intervention or study participation, the investigator must promptly notify the sponsor.

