# 6.4. Reference Start Date and Study Day

Study Day will be calculated from the reference start date and will be used to show start/stop day of assessments and events. It will appear in every listing where an assessment date or event date appears. Reference start date is defined as the day of study medication administration (Day 1 is the day of the study medication administration).

- If the date of the event is on or after the reference date, then:
- Study Day = (date of event reference date) + 1.
- If the date of the event is prior to the reference date, then:
   Study Day = (date of event reference date).

In the situation where the event date is partial or missing, the date will appear partial or missing in the listings, and Study Day, and any corresponding durations will be presented based on the imputations specified in APPENDIX 2.

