# APPENDIX 2. PARTIAL DATE CONVENTIONS

# **Algorithm for Treatment Emergence of Adverse Events:**

START DATE	STOP DATE	ACTION
Known	Known/Partial/ Missing	If start date < study med start date, then not TEAE  If start date >= study med start date, then TEAE
Partial, but known components show that it cannot be on or after study med start date	Known/Partial/ Missing	Not TEAE
Partial, could be on or after study med start date OR Missing	Known	If stop date < study med start date, then not TEAE  If stop date >= study med start date, then TEAE
	Partial	Impute stop date as latest possible date (i.e. last day of month if day unknown or 31st December if day and month are unknown), then:  If stop date < study med start date, then not TEAE

[figure not shown]
Page 40 of 42

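### SAP 18.1 ends the TEAE window at Day 71 and Appendix 2 sets no end, so an AE starting on Days 72 to 74 can be classed two ways

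*SAP*

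**What the plan says.** **SAP 18.1 (Adverse Events)** defines a TEAE as an AE that first occurs or gets worse after dosing, "up to Day 71 (including the follow-up period) after the study medication administration". SAP 6.4 fixes the day count: "Day 1 is the day of the study medication administration".

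**Protocol 1.1 and 4.1** give the last visit a window: "A final follow-up visit on Day 71 (± 3 days"). The schedule in Protocol Table 1.3-1 shows the same allowance. **Protocol 8.4.1** ties AE collection to that visit rather than to a fixed day: "All AEs and SAEs will be collected from the signing of the ICF until the last visit".

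**SAP Appendix 2** contains a treatment-emergence algorithm. Its row for a known start date says "If start date >= study med start date, then TEAE". Where the start date is partial and could fall on or after dosing, or is missing, the test moves to the stop date: "If stop date >= study med start date, then TEAE". If the stop date is missing too, the AE is assumed to be a TEAE. No branch has an upper limit.

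**The concern.** The SAP states two rules for the end of the TEAE window, and they disagree for a few days on which the protocol expects AEs to be recorded. A final visit on Day 72, 73 or 74 is within the visit allowance and is not a deviation, so an AE with onset on one of those days is properly collected. A programmer following 18.1 to the letter would leave it out of the TEAE tables; one following Appendix 2 would include it.

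TEAE incidence is a primary endpoint, and the unsolicited AE tables in SAP 18.1.1.2 are built on TEAEs. The days in question can include the final visit itself, when safety laboratory tests and a full physical examination are scheduled. Under Protocol 8.3.4 a clinically significant laboratory change is recorded as an AE, so a new finding dated to a late final visit would fall in the gap.

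Groups are small. With 7 active participants per dose level, moving one participant in or out of a row changes that incidence by 1/7, or 14 percentage points. If the rule is not settled until such an event turns up, it will be chosen with the event in view.

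**Working it through.** **1. Is Day 74 planned conduct?** The protocol's own maximum duration answers this. Protocol 4.1 says "The total duration of the clinical study per participant will be up to 102 days", and screening is "A screening visit up to 28 days before dosing".

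- Screening + final visit + upper allowance: 28 + 71 + 3 = 102 days, which reproduces the stated figure.
- Without the allowance: 28 + 71 = 99 days, which does not.

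So the protocol counts on final visits up to Day 74.

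**2. Apply both rules to a known onset date.** Dosing is Day 1.

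| Onset day | Collected, if the last visit is on Day 74 | 18.1, cut-off Study Day 71 | 18.1, cut-off 71 days after dosing (Study Day 72) | Appendix 2 |
|---|---|---|---|---|
| 68 to 71 | yes | TEAE | TEAE | TEAE |
| 72 | yes | not TEAE | TEAE | TEAE |
| 73 | yes | not TEAE | not TEAE | TEAE |
| 74 | yes | not TEAE | not TEAE | TEAE |

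The rules disagree on 3 of 74 post-dose days (3/74 = 4.1%), or on 2 of 74 (2.7%) under the later cut-off. Both cut-offs are possible because 18.1 names a study day and then adds that it is counted after dosing. SAP 13 counts 71 days after study medication for concomitant medications, which is Study Day 72.

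**3. Does the worst-case fallback settle it?** No. In 18.1 it applies only when an AE cannot be classified. An AE with a known Day 73 onset can be classified; the two rules simply give different answers.

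**4. How many events?** The documents give no AE rate and no distribution of visit days. I therefore assume a constant rate of r AEs per participant over 74 days, with r from 0.5 to 2, and that all 54 participants reach the final visit.

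Expected AEs in the gap = 54 × r × (mean days observed after Day 71) / 74.

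- *Visits spread evenly over Days 68 to 74.* Mean days after Day 71 = (0 + 0 + 0 + 0 + 1 + 2 + 3)/7 = 6/7 = 0.86.
  - r = 0.5: 54 × 0.5 × 0.857/74 = 0.31
  - r = 1: 0.63
  - r = 2: 1.25
- *Every participant attends on Day 74* (upper extreme). Mean days = 3.
  - r = 0.5: 54 × 0.5 × 3/74 = 1.1
  - r = 1: 2.2
  - r = 2: 4.4

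**5. After the fix.** If 18.1 runs to the actual last visit, the two rules agree for every known post-dose onset in the collection period. The number of discordant days falls from 3 to 0.

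**The case against.** The strongest reply is that 18.1 already means what the protocol means. Its parentheses bring in the follow-up period, and the protocol calls the last visit a follow-up visit. Day 71 is also the nominal label of that visit in the schedule and in SAP Appendix 1, and SAP 6.6 presents data by nominal visit. On that reading the window runs through the final visit whenever it is held, and there is no conflict. This may well be the intent, and for that reason the documents do not support saying that AEs on Days 72 to 74 are definitely excluded. But the sentence names a day, not a visit, and it governs event onset dates, which are not mapped to nominal visits. The ambiguity stands.

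A second reply is that Appendix 2 is titled as a partial-date convention, is cited in 18.1 for that purpose, and mainly separates pre-dose from post-dose onset. It can be read as subordinate to 18.1. That is fair, but its first row gives a rule for fully known dates. If 18.1 prevails, its literal cut-off also falls short of the protocol's collection period.

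A reader might further infer that final-visit findings would drop out of the primary safety evaluation. They would not. Laboratory tests and physical examinations are primary safety variables in their own right. Their by-visit change and shift tables (SAP 18.2 and 18.5) do not depend on TEAE status and keep a late final visit under its nominal label. All AEs are listed (Protocol 9.2.2.1), and SAEs and deaths have separate listings. Injection site reactions are last assessed at the Day 29 visit, well before the gap.

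**Conclusion.** The point holds as an unresolved inconsistency about the end of the TEAE window, and it is minor. Read literally, AEs with onset on Days 72 to 74 (Days 73 and 74 under the later cut-off) fall outside 18.1 and inside Appendix 2. Only the TEAE incidence tables are exposed.

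The likely size is about 0 to 1 event in the study: 0.3 to 1.3 AEs with evenly spread visits, and 1.1 to 4.4 in the extreme case that everyone attends on Day 74. These figures rest on the assumed 0.5 to 2 AEs per participant, a constant rate over 74 days and no dropout; none of these comes from the documents.

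It would be tempting to note that 3 of 7 possible visit days (43%) fall after Day 71, and to quote about 23 of 54 participants as affected. That is not a measure of impact. It counts visits that might be late under an assumed even spread, not participants with a new AE on those days.

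No dose-escalation decision or hypothesis test depends on this. The SMC review is triggered once at least 7 participants have completed 14 or more days, its reporting lies outside the SAP, and no formal testing is planned. It is still worth correcting, because it concerns a primary endpoint in groups of 7 and the correction costs almost nothing.

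**What to change.** In SAP 18.1, define TEAEs as AEs that start or worsen in severity from study medication administration through the participant's actual last study visit, including an early termination visit. Put the same upper limit in the Appendix 2 treatment-emergence algorithm, including its partial-date and missing-date branches, and keep the existing worst-case rule for AEs that cannot be classified.

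This matches the collection period in Protocol 8.4.1 and also removes the question of whether the cut-off is Study Day 71 or 72. The cost is one sentence in 18.1, a matching limit in Appendix 2 and the corresponding line of programming. No protocol change or new data collection is needed. It should be settled before database lock and unblinding, so that the rule is not chosen with the events in view.

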#### 18.1.1. All TEAEs

Incidence of TEAEs will be presented by SOC and PT and broken down further by maximum severity and relationship to study medication.

#### 18.1.1.1. SEVERITY

Severity is classed as mild/ moderate/ severe/ potentially life threatening (increasing severity) as judged by

Visterra Insert
Customer Name/ Logo
Protocol VIS954-101
Page 32 of 42

Statistical Analysis Plan

the investigator per protocol requirements. TEAEs starting after the study medication administration with a missing severity will be classified as severe. If a participant reports a TEAE more than once within that SOC/PT, the AE with the worst-case severity will be used in the corresponding severity summaries.

#### 18.1.1.2. RELATIONSHIP TO STUDY MEDICATION

Relationship, as indicated by the Investigator per protocol requirements, is classed as "related" or "not related". A "related" TEAE is defined as a TEAE with a relationship to study medication assessed as "related" by the Investigator based on if there is a reasonable possibility of a temporal and causal relationship between study intervention and the AE. TEAEs with a missing relationship to study medication will be regarded as "related" to study medication. If a participant reports the same AE more than once within that SOC/PT, the AE with the worst-case relationship ("related") to study medication will be used in the corresponding relationship summaries.

All AE tabulations will be performed by dose level, for all active-treated participants, and overall participants; and will include the number and percentage of participants. AEs for participants treated with placebo from all cohorts will be pooled together in a single placebo group. Incidence of unsolicited TEAEs will be tabulated by the following:

- Across all SOC and PT, By Severity, by Relationship, by Leading to Study Discontinuation, and by Seriousness.
- By SOC and PT.
- By SOC, PT and Maximum Severity.
- By SOC, PT for AEs Related to study medication only.
- By SOC, PT and Maximum Severity for AEs Related to study medication.
- By SOC, PT and participants' Overall ADA Status.

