8.10 Health Economics or Medical Resource Utilization and Health Economics

Health economics or medical resource utilization and health economics parameters are not evaluated in this study.

Clinical Study Protocol VIS954-101

9 Statistical Considerations

The statistical analysis plan will be finalized prior to database lock and it will include a more technical and detailed description of the statistical analyses described in this section. This section is a summary of the planned statistical analyses of the most important endpoints including primary and key secondary endpoints.

In general, descriptive statistics for continuous variables will be summarized by treatment group using number of participants, arithmetic mean, standard deviation, median, minimum and maximum; descriptive statistics for categorical data will be summarized by treatment group using frequency counts and percentages. The placebo participants will be pooled into a single placebo group for summaries and presentations. Therefore, treatment group will refer to each of the dose level of VIS954 and pooled placebo.

Adverse events, clinical laboratory tests, vital sign measurements, ECGs, physical examinations, and injection site reactions are the primary endpoints of the study. All AEs will be coded by Medical Dictionary for Regulatory Activities (MedDRA) system organ class and preferred term.

The incidence of TEAEs will be summarized by treatment group.

Participants with clinically significant abnormalities in clinical laboratory tests, vital signs, physical examinations, and injection site reactions will be summarized by count and percentage.

In general, missing data will be left missing, analyses will be conducted based on the available cases and will be clearly reflected by reporting a category of "NOT REPORTED" or reflected in the total number of participants used for analysis.

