9.2.2 Safety Analysis

9.2.2.1 Adverse Events

Adverse events will be coded by system organ class and preferred term using the Medical Dictionary for Regulatory Activities (MedDRA). All AEs will be listed.

The incidence of the following events will be summarized:

- TEAEs
- TEAEs by severity
- Serious TEAEs
- TEAEs leading to discontinuation of the study intervention
- Serious TEAEs leading to discontinuation of the study intervention

The categories of the relationship to study intervention will be summarized as related and not related.

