# 2.1. Primary Objective and Endpoints

Objectives	Endpoints
Primary:  To evaluate the safety and tolerability of VIS954 in healthy participants	Primary: Safety The following safety variables will be assessed: Incidence of TEAEs Physical examinations Vital sign measurements (blood pressure, pulse, body temperature, and respiratory rate)  12-Lead ECGs Clinical safety laboratory tests (hematology, clinical chemistry, coagulation, and urinalysis) Injection site reactions and Wong-Baker FACES Pain Rating Scale

ECG = electrocardiogram; TEAEs = treatment-emergent adverse events.

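### The listed TEAE tables cover unsolicited events only, so no described output gives the incidence of any TEAE, or any related TEAE, with solicited and unsolicited events combined

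*SAP*

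**What the plan says.** **Protocol.** Incidence of TEAEs is the first item under the primary objective. The opening of Section 9 states "The incidence of TEAEs will be summarized by treatment group" and "All AEs will be coded by Medical Dictionary for Regulatory Activities (MedDRA) system organ class and preferred term". Section 9.2.2.1 begins its list with "The incidence of the following events will be summarized" and names TEAEs, TEAEs by severity and serious TEAEs, among others. It then asks for a related/not related summary. None of this is confined to unsolicited events.

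**SAP, unrestricted text.** Section 18.1: "Treatment-emergent adverse events (TEAEs) are defined as AEs that first occur or worsen in severity after the study medication administration", up to Day 71. Section 18.1.1, headed All TEAEs: "Incidence of TEAEs will be presented by SOC and PT and broken down further by maximum severity and relationship to study medication".

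**SAP, restricted text.** Section 18.1 on coding: "Unsolicited Adverse Events (AEs) will be coded using MedDRA central coding dictionary, version 26.1". Section 18.1.1.2 on the tables: "Incidence of unsolicited TEAEs will be tabulated by the following". Six tabulations follow:
- an overall summary by severity, relationship, study discontinuation and seriousness;
- SOC/PT;
- SOC/PT by maximum severity;
- SOC/PT for related events;
- SOC/PT by maximum severity for related events;
- SOC/PT by ADA status.

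**SAP, solicited events.** The primary endpoint list in Section 2.1 has its own item, "Injection site reactions and Wong-Baker FACES Pain Rating Scale". Section 18.1.2 tabulates injection-site reactions by type, severity, timepoint and treatment group, and also over all timepoints, for all VIS954 groups and for all participants. A stacked bar graph shows participants with any reaction by severity.

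**The concern.** The SAP gives two different scopes for the same endpoint and does not say which governs. One programmer could follow 18.1.1 and count every TEAE. Another could follow 18.1.1.2 and count only unsolicited ones. Both would label the result as TEAE incidence.

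Under the restricted reading, the overall and related-event figures of a first-in-human subcutaneous study exclude reactions found at the scheduled injection-site checks. Those are the events most directly tied to the injection. Protocol 8.4 and 10.3.4 presume events to be related unless another cause is obvious, so a related-TEAE table without these reactions answers a narrower question than its title suggests. A reader who wants the proportion of participants with any TEAE, or any related TEAE, could not get it from the described tables.

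**Working it through.** The question is which events enter which tables, so the first part of the check is textual.

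1. **Are solicited reactions TEAEs?** Protocol 10.3.1 and SAP 18.1 both treat solicited events as adverse events. The injection-site checks are all after dosing (1, 4 and 24 hours, Days 3 and 29), so a reaction first seen at one of them first occurs after administration. It meets the SAP's TEAE definition.
2. **Do they enter the SOC/PT tables?** Under 18.1.1, yes. Under the list in 18.1.1.2, no. With coding stated only for unsolicited events, solicited ones would have no SOC or PT to be tabulated under.
3. **Does 18.1.2 fill the gap?** For reaction type and severity, yes. It describes no breakdown by relationship, seriousness or ADA status, and no count combined with unsolicited events.
4. **Are solicited systemic events covered?** SAP 18.1 includes them in the definition of solicited events. The reactions listed in 18.1.2 are injection-site reactions only. No table is stated for solicited systemic events.
5. **Is the change declared?** The readable part of SAP 3.3 does not mention it. One bullet there is redacted, so this is weak evidence.

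The second part is an illustration. The documents give no TEAE or reaction rates, so there is no plan figure to reproduce and every rate below is assumed. Let u be the proportion of participants with an unsolicited TEAE and s the proportion with a solicited one. If the two are independent,

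combined incidence = 1 − (1 − u)(1 − s).

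The number on VIS954 is 6 cohorts × 7 = 42.

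| u | s | Combined | Difference from u | Participants of 42 |
|---|---|---|---|---|
| 40% | 20% | 1 − 0.60 × 0.80 = 52% | 12 points | 0.12 × 42 = 5.0 |
| 60% | 5% | 1 − 0.40 × 0.95 = 62% | 2 points | 0.02 × 42 = 0.8 |
| 20% | 40% | 1 − 0.80 × 0.60 = 52% | 32 points | 0.32 × 42 = 13.4 |

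The second and third rows are the smallest and largest differences for u from 20% to 60% and s from 5% to 40%.

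Independence is itself an assumption. At u = 40% and s = 20%, the combined figure is 40% if every participant with a solicited event also has an unsolicited one, and 40% + 20% = 60% if none does. The separate tables therefore bound the combined incidence but do not determine it.

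**The case against.** The strongest reply is that separate tabulation follows the protocol's own structure. Injection-site reactions are a separate primary item, and Protocol 9.2.2.5 gives them their own descriptive analysis. No hypothesis is tested, and SMC reporting is outside the SAP. All of this stands, and it rules out three stronger conclusions that a reader might draw.

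- **That the primary safety analysis drops injection-site reactions.** It does not. SAP 18.1.2 reports them by severity and over all timepoints.
- **That a severe or serious reaction would go unreported.** A severe one appears in the 18.1.2 severity summaries. Events recorded as serious on the AE page are listed under 18.1.4 with no restriction to unsolicited events. At most, a reaction would be missing from a summary count.
- **That the headline TEAE figure is understated by a known amount.** The documents give no rates, and the illustration takes its size from its assumptions.

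A further reply is that the exclusion is not certain. Section 18.1.1 is unrestricted, and the output templates, which fix table content, are not available here. The protocol also defines an unsolicited event as one not solicited through a participant diary, and the schedule as shown includes no diary. Read literally, that could make every event unsolicited. A reaction reported outside the scheduled checks could likewise be recorded as unsolicited and enter the tables. This weakens any claim that every injection-site reaction is excluded. It also shows that the boundary needs to be settled in the SAP.

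None of these replies supplies a combined participant-level count or a relationship summary for solicited reactions.

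**Conclusion.** The point holds as an internal conflict with a specific consequence. SAP 18.1.1.2 and the coding sentence in 18.1 are narrower than SAP 18.1.1, the SAP's TEAE definition and the protocol's provisions on TEAE incidence, coding and relationship. If the listed tables are followed, no described output gives the incidence of any TEAE or any related TEAE across solicited and unsolicited events, and solicited systemic events have no stated table.

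The conclusion rests on reading the 18.1.1.2 list as the operative one, and on the visible text of both documents. The numerical effect cannot be stated from the documents: 52% against 40% is an example under assumed rates and independence. Nothing inferential is affected.

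**What to change.** In SAP 18.1 to 18.1.2:

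- Reconcile 18.1.1 with 18.1.1.2, so that one scope governs the TEAE tables. State how a reaction is classed as solicited or unsolicited without relying on a diary.
- Code all adverse events in MedDRA, as the protocol requires. Include solicited reactions and the category of other injection-site reactions in 18.1.2.
- Base the overall TEAE summary (any, by maximum severity, related, serious, leading to discontinuation) and the SOC/PT table on all TEAEs, counting each participant once.
- Keep the unsolicited-only and solicited-only tables as subsets, and name a table for any solicited systemic events.

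The cost is SAP wording, minor coding and a few added rows. Protocol 10.3.4 already requires a causality assessment for each adverse event. The documents do not show whether the injection-site form records it. Where it is not recorded for a solicited reaction, the existing rule in SAP 18.1.1.2, which counts a missing relationship as related, applies.
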